13.8 Study drug restart after temporary treatment interruption

Study drug should be reintroduced in those who temporarily discontinue it as soon as medically justified in the opinion of the Investigator and at the most appropriate and allowable dose level per his/her medical judgment. Should the subject not tolerate the re-start study drug dose level, he/she may be down-titrated again (if appropriate) or discontinue the study medication again and a new attempt to up-titrate or reintroduce the study drug could be considered by the Investigator as soon as medically justified in his/her medical judgment.

13.9 Study drug discontinuation and premature withdrawal of subjects

After randomisation, study drug discontinuation for any reason does not constitute withdrawal from the study and should not lead to the subject being withdrawn from the entire study. On the contrary, even subjects who have stopped taking study drug are expected to attend all the protocol specified study visits and perform all assessments as stipulated in the visit schedule (Table 2). If the subject does not attend the study visits, follow-up should continue according to the specified schedule by telephone to determine if any of the health events/endpoint prespecified in the protocol has occurred, except in the case that the subject specifically refuses such follow-up and withdraws his/her consent. The emergence of the following circumstances will require study drug discontinuation:

- Subject wishes to withdraw from study with or without stated reason
- Pregnancy
- Investigator thinks that continuation would be detrimental to the subject's well-being
- Suspected occurrence of angioedema

Study medication may be discontinued at the Investigator's discretion if any of the following occurs:

- Any subject who experiences an AE may be withdrawn at any time from the study at the discretion of the Investigator. However, the following AE warrants immediate withdrawal;
 - Angioedema: if angioedema (including swelling of the larynx and glottis, causing airway obstruction and/or swelling of the face, lips, pharynx, and/or tongue) occurs, study drug should be immediately discontinued and appropriate therapy and monitoring should be provided until complete and sustained resolution of signs and symptoms has occurred. Study drug must not be re-administered.
 - Serious hypersensitivity reactions
- Depending on the serum potassium, blood pressure, or eGFR, subjects may need to have their study drug dose or the dose of another concomitant medication reduced or discontinued, or, if appropriate, have potentially contributing agents adjusted. Please refer to Appendices 7-10 for treatment guidelines for hyperkalaemia, hypotension, or renal dysfunction.

In the case of study drug discontinuation, the subject should continue to complete all scheduled study visits and procedures. If the subject refuses, he/she should be contacted by telephone in place of protocol-specified visits unless the subject expressly refuses such contacts. A record of all attempts to contact the subject should be recorded in the Telephone Contact Log in the CRF.

If a subject is withdrawn from the study due to an AE, the AE should be noted on the appropriate CRF and the subject's progress should be followed until the AE is resolved. This follow-up may occur by phone.

13.10 Emergency unblinding of treatment assignment

Emergency unblinding should only be undertaken if knowledge of the subject's trial treatment affects the immediate, urgent medical treatment of the subject. Most often, study drug discontinuation and knowledge of the possible treatment assignments are sufficient to treat a study subject who presents with an emergency condition.

If the treatment allocation needs to be revealed, contact the WebEz Helpdesk as per the process outlined in the SOP 'Unblinding of the Study Drug during PARABLE by the Investigator' (HBT-GCP-SOP-12)

Study drug must be discontinued after emergency unblinding. Study drug also must be discontinued for any subject whose treatment code has been broken inadvertently or for any non-emergency reason and the investigator becomes aware of the treatment allocation.

13.11 Definition of end-of-trial

The end-of-trial is the date of the last visit of the last subject enrolled in the 9-month follow-up sub-study.

Other end of study considerations

The Sponsor or Principle Investigator has the right at any time to terminate the study for clinical or administrative reasons. In terminating the study, the Sponsor and the Principle Investigator will ensure that adequate consideration is given to the protection of the best interests of the participants.

The end of the study will be reported to the Ethics Committee (EC) and Regulatory Authority within 90 days, or 15 days if the study is terminated prematurely. The Investigators will inform subjects and ensure that the appropriate follow-up is arranged for all involved.

A summary report of the study will be provided to the sponsor (Novartis), the EC and HPRA within 12 months of the end of the study. This is a legal requirement. The final study report shall include a full summary of safety and efficacy information from the study and shall comply with the established principles and standards for the corresponding format according to ICH-GCP.

14. SAFETY REPORTING

The safety and tolerability of the study drugs will be evaluated starting from the administration of the study drug (Visit 2) through to EOS visit. Information regarding all AEs will be collected at each study visit based on information provided spontaneously by the subject and/or through questioning of the subject.

14.1 Definitions

Adverse event (AE)

Any untoward medical occurrence in a patient or clinical trial subject administered a medicinal product and which does not necessarily have a causal relationship with this treatment. An AE can therefore be any unfavourable and unintended sign (including an abnormal laboratory finding, for example), symptom or disease temporally associated with the use of a medicinal product, whether or not considered related to the medicinal product.

Worsening of a pre-existing medical condition (e.g., cancer, diabetes, migraine headaches, gout) should be considered an AE if there is either an increase in severity, frequency, or duration of the condition or an association with significantly worse outcomes. Abnormal signs and symptoms identified during the physical and cardiac exam may also constitute an adverse event if they were not present at baseline. Interventions for pre-treatment conditions (e.g., elective cosmetic surgery) or medical procedures that were planned before study enrolment are not considered AEs.

The Investigator is responsible for reviewing laboratory test results and determining whether an abnormal value in an individual study subject represents a change from values before the study. In general, abnormal laboratory findings without clinical significance (based on the Investigator's judgment) should not be recorded as AEs; however, laboratory value changes requiring therapy or adjustment in prior therapy are considered AEs.

All AEs are recorded in the CRF and on the Adverse Event Report Form within the CRF.

Adverse reaction (AR)

All untoward and unintended responses to a medicinal product related to any dose. The phrase 'responses to a medicinal product' means that a causal relationship between a study medication and an AE is at least a reasonable possibility, i.e., the relationship cannot be ruled out. All cases judged by either the reporting medically qualified professional or the Sponsor as having a reasonable suspected causal relationship to the study medication qualify as adverse reactions.

All ARs are recorded in the CRF and on the Adverse Event Report Form within the CRF.

Serious adverse event (SAE)

Any untoward medical occurrence or affect that at any dose:

- results in death,
- is life-threatening*
- requires hospitalisation[‡] or prolongation of existing hospitalisation
- results in persistent or significant disability or incapacity
- is a congenital anomaly or birth defect
- important medical events**

[‡] A hospitalisation meeting the regulatory definition for “serious” is any inpatient hospital admission that includes a minimum of an overnight stay in a health care facility. Any AE that does not meet one of the definitions of serious (e.g., A & E visit, outpatient surgery, or requires urgent investigation) may be considered by the Investigator to meet the “other significant medical hazard” criterion for classification as a serious adverse event.

*Regarding a life-threatening event, this refers to an event in which the subject was at risk of death at the time of the event; it does not refer to an event which hypothetically might have caused death if it were more severe.

**Some medical events may jeopardise the subject or may require an intervention to prevent one of the above characteristics/consequences. Such events (hereinafter referred to as ‘important medical events’) should also be considered as ‘serious’ in accordance with the definition.

All SAEs are recorded in the patients’ medical notes, the CRF, on the Adverse Event Report Form within the CRF and on a Serious Adverse Event Report Form (HBT-GCP-FM-21).

Severe adverse events

The term ‘severity’ is used here to describe the intensity of a specific event. This has to be distinguished from the term ‘serious’.

The severity of the AE should be graded according to the following definitions:

- *Mild*: An event that is easily tolerated by the subject, causing minimal discomfort and not interfering with everyday activities
- *Moderate*: An event that is sufficiently discomforting to interfere with normal everyday activities
- *Severe*: An event that prevents normal everyday activities

Suspected unexpected serious adverse reactions (SUSAR)

An adverse reaction, the nature or severity of which is not consistent with the applicable product information (e.g. Investigator’s brochure for an unauthorised investigational medicinal product or summary of product characteristics (SmPC) for an authorised medicinal product.

14.2 Adverse event assessment

Assessment of seriousness

The Investigator should make an assessment of seriousness (see definition of seriousness in section 14.1).

Assessment of causality

All adverse events judged by either the Investigator or the Sponsor as having a reasonable suspected causal relationship to an investigational medicinal product qualify as adverse reactions.

As the PARABLE study is blinded, the case should be assessed for causality assuming that the study drug under investigation caused the reaction (i.e. LCZ696).

The causality assessment given by the Investigator should not be downgraded by the Sponsor.

The Investigator/Sponsor must make an assessment of whether the AE/SAE is likely to be related to treatment according to the following definitions:

- *Unrelated:* Where an event is not considered to be related to the study medication.
- *Possible:* Although a relationship to the study medication cannot be completely ruled out, the nature of the event, the underlying disease, concomitant medication or temporal relationship make other explanations possible.
- *Probable:* The temporal relationship and absence of a more likely explanation suggest the event could be related to the study medication.

All AEs/SAEs judged as having a reasonable suspected causal relationship (e.g. possible, probable) to the study medication will be considered as ARs/SARs.

All AEs/SAEs judged as being related (e.g. possibly, probably) to an interaction between the study medication and another medication will also be considered to be ARs/SAR.

Alternative causes such as natural history of the underlying disease, concomitant therapy, other risk factors and the temporal relationship of the event to the treatment should be considered.

Assessment of severity

The Investigator will make an assessment of severity for each AE/SAE and record this on the Adverse Event Report Form according to one of the following categories:

- *Mild*: An event that is easily tolerated by the subject, causing minimal discomfort and not interfering with every day activities.
- *Moderate*: An event that is sufficiently discomforting to interfere with normal everyday activities.
- *Severe*: An event that prevents normal everyday activities.

Assessment of expectedness

The expectedness of an adverse reaction will be determined by the Sponsor according to the reference document which in this study is the Investigator's brochure for LCZ696 and the SmPC for valsartan.

14.3 Emergency unblinding procedures

See section 13.10.

14.4 Follow up of adverse events

It will be left to the Investigators clinical judgement whether or not an AE is of sufficient severity to require the subject's removal from treatment. A subject may also voluntarily withdraw from treatment due to what he or she perceives as an intolerable AE. If either occurs, the subject must undergo an EOS assessment and be given appropriate care under medical supervision until symptoms cease or the condition becomes stable.

All SAEs that are encountered during the reporting period will be followed to their resolutions, until the Investigator assesses them as stable.

AEs considered related to the study medication as judged by the Investigator or Sponsor will be followed until resolution or until the subject/event is considered stable.

All related AEs that result in a subject's withdrawal from the study or are present at the end of the study, should be followed up until a satisfactory resolution occurs.

Any pregnancy occurring during the clinical study and the outcome of the pregnancy should be recorded and followed-up for congenital abnormality or birth defect.

14.5 Documentation of adverse events by the Investigator

All AEs occurring during the study, observed by the Investigator or reported by the subject, whether or not attributed to the study medication are recorded in the appropriate section of the CRF.

All AEs are also recorded on an Adverse Event Report Form within the CRF.

In addition to recording the AE in the CRF and on an Adverse Event Report Form, all SAEs must be recorded on a Serious Adverse Event Report Form (HBT-GCP-FM-21). and in the patients' medical file.

The following information shall be recorded on the Adverse Event Report Form.

- AE event term
 - Whenever possible, recognized medical terms will be used to describe AEs rather than colloquialisms (for example, “influenza” rather than “flu”) and abbreviations will be avoided.
- A description of the event
- Dates of onset and resolution
- The maximum severity of the AE (i.e. mild, moderate or severe)
- The relationship (causality) of the event to the study drug should be determined by the Investigator (Unrelated, possibly related, probably related)
- Any drug action taken by the Investigator to resolve the event:
 - None
 - Dose reduced
 - Dose increased
 - Withdrawn permanently
 - Withdrawn temporarily
 - Unknown
 - Other (which can include concomitant medication given, non-drug therapy given or hospitalized etc).
- Event outcome at resolution or time of last follow-up will be recorded as:
 - Recovered without sequelae
 - Recovered with sequelae
 - Not yet recovered
 - Unknown
 - Fatal
- Seriousness. AEs shall be assessed as serious or non-serious according to the definition in section 14.1.

AEs occurring secondary to other AEs (e.g. sequelae or complications) will be identified by the primary cause. A primary AE if clearly identifiable, generally

represents the most accurate clinical term to record. The Investigator will provide his/her opinion of which is the primary AE.

14.6 Reporting procedures for SAEs to the Sponsor

See Appendix 7 for an overview of this procedure.

All SAE information must be recorded on an SAE Report form and forwarded (by fax, email or in person) to the sponsor (Clinical Trial Project Manager) within 24 hours. Under no circumstances should this exceed **24 hours** following knowledge of the SAE.

Additional information received for a case (follow-up or corrections to the original case) need to be detailed on a new SAE form and sent expeditiously to the Sponsor.

The Sponsor will keep detailed records of all adverse events which are reported to him by the Investigator or Investigators and perform an evaluation with respect to seriousness, causality and expectedness. If the Sponsor disagrees with the Investigators assessment, both the opinion of the Investigator and the Sponsor should be provided with the report. The Sponsor should NEVER downgrade any assessment made by the Investigator.

14.7 Reporting procedures for SUSARs to the EC and Regulatory authorities

The Sponsor will report all SUSARs in parallel to both the competent authorities (the Health Products Regulatory Authority (HPRA) in Ireland) and the Clinical Trials module of the EudraVigilance database (EVCTM) and to the EC(s) concerned. For HPRA reporting, an electronic transmission will be sent via EudraVigilance.

As a back-up measure during times of non-availability of the clinical trials project manager, the reporter shall report the SUSAR to the HPRA directly using the online report form at the following address:

<https://www.hpra.ie/homepage/about-us/report-an-issue/form2>

This arrangement has been agreed with the Pharmacovigilance Department of the HPRA. They have requested that all SUSARs be transmitted to them in a timely manner in order to facilitate internal HPRA review and onward reporting by the HPRA to EudraVigilance. The following timelines therefore, must be adhered to:

- Any fatal/life threatening reports must reach the HPRA by Day 2.
- All other SUSARs by Day 7.

During any planned absences, the CTPM shall confirm in writing to the Principal Investigator and the Investigator team the process to be followed, including who to contact to carry out an assessment of expectedness. During any unplanned absences, the Research Director of the Heartbeat Trust should be contacted.

For EC reporting to the St Vincent's EC, a copy of the SAE Report Form along with a cover letter should be emailed to [contact].

Timelines for reporting

- Fatal or life-threatening SUSARs must be reported within **7 days**.
- SUSARs which are not fatal and not life-threatening are to be reported within **15 days**.

The Sponsor will also inform all Investigators concerned of relevant information about SUSARs that could adversely affect the safety of subjects.

If the initial report is incomplete, e.g. if the Sponsor has not provided all the information/assessment within seven days, the Sponsor will submit a completed report based on the initial information within an additional eight days.

If significant new information on an already reported case is received by the Sponsor, the clock starts again at day zero, i.e. the date of receipt of new information. This information will be reported as a follow-up report within **15 days**.

14.8 SAE reporting to Novartis

See Appendix 8 for an overview of this procedure.

The Sponsor shall provide to Novartis details of all SAEs irrespective of causality within 24 hours of first notification of the SAE or subsequent follow-up information to the Sponsor.

Initial and follow-up reports shall be emailed or faxed directly to the Novartis Safety Desk in Ireland:

Novartis Ireland Limited Drug Safety and Epidemiology [name] [contact] [contact] Email: CC: [contact]
--

To facilitate Novartis' compliance with the regulatory requirements, all suspected unexpected SAEs will be unblinded for regulatory reporting.

The Sponsor shall support Novartis in the following-up of all SAEs. The Sponsor shall perform SAE reconciliation according to Novartis SOPs and processes on an ongoing basis throughout the study.

SAEs will be reviewed on an ongoing basis by the Sponsor or its designee, with a summary included in the annual reports to regulatory agencies and analysis will be provided in the final study report.

14.9 Annual reports and line listings

In addition to the expedited reporting above, the Sponsor shall submit once a year throughout the clinical trial or on request, a safety report to the competent authority (the HPRA in Ireland) and EC. The annual safety report will be presented in the DSUR format as per ICH guideline E2F - Note for guidance on development safety update reports. This is a legal requirement. (See also SOP: HBT-GCP-SOP-09)

The Sponsor shall provide the St Vincent's EC with six monthly line listings of all SAEs (whether suspected or not, or unexpected or not) which have occurred over the reporting period.

Line listings are not routinely required by the HPRA. However, it should be noted that copies of these line listings may be requested and, as such, should be made available to the HPRA when required.

15. PROTOCOL ADHERENCE

Investigators ascertain they will apply due diligence to avoid protocol deviations.

If the Investigator feels a protocol deviation would improve the conduct of the study this must be considered a protocol amendment, and unless such an amendment is agreed upon by the Sponsor and approved by the applicable Health Authorities and EC, it cannot be implemented. Therefore, all suggested protocol deviations must be communicated to the Sponsor who will decide whether or not to submit an amendment to the protocol.

Once identified, the investigator shall record the deviation in the Deviation Log (HBT-GCP-FM-28) as per SOP HBT-GCP-SOP-05; 'Deviation Management'.

15.1 Protocol Amendments

Any change or addition to the protocol can only be made in a written protocol amendment that must be approved by the Sponsor, Health Authorities and EC. Only amendments that are required for subject safety may be implemented prior to approval. Notwithstanding the need for approval of formal protocol amendments, the Investigator is expected to take any immediate action required for the safety of any subject included in this study, even if this action represents a deviation from the protocol. In such cases, the Sponsor should be notified of this action and the EC informed within 10 working days.

16.2 Determination of sample size

Based on the endpoint of change in LAVI over 18 months, the PARABLE trial aims to recruit 250 subjects (125 per arm). The current STOP-HF database includes 1499 subjects with cardiovascular risk factors. An additional cohort of just under 1000 subjects has been recruited from the STOP-HF outreach service and is available for screening and recruitment into the study. The STOP-HF Investigators are also working with other clinical trial units and can incorporate additional centres if required to achieve timely recruitment.

Sample size estimates were calculated from the current STOP-HF subject database (n=1499). A subsample of subjects with BNP > 50 pg/mL, LAVI > 28 mL/m², with normal EF (\geq 50%) and in normal sinus rhythm was drawn. This resulted in a population of 163 (11%) of the total with a population BNP of 125 pg/mL and a baseline mean LAVI of 36.2 mL/m² (standard deviation of 6.9 mL/m²) determined by Doppler

Echocardiography. This LAVI is reassuringly similar to the baseline level observed by Solomon et al. (Lancet 2012; 380: 1387–95) in the PARAMOUNT study, which observed a 36-week drop in LAVI of 2.6 mL/m², and assuming the control group shows no decrease in LAVI (as in Solomon et al. 2012 paper), the expected effect size in a similar study is $2.6/6.5 = 0.38$. Setting alpha = 5% (two-tailed), beta = 20% and using an independent t-test to assess the change in LAVI over follow-up, the required number of subjects to detect this effect is 222 (111 per study arm), or 248 after accounting for a 10% dropout rate.

In a review of the expected effect size, once blinded echocardiography was available for 125 patients at the 9-month time point, it was noted that the actual standard deviation of baseline to 9-month change scores was 4.7. This means an expected effect size of at least $(2.0/5.0) = 0.40$. An effect size of 0.4 would require 96 patients in each group, suggesting that the study is adequately powered on LAVI assessed by echocardiography. In addition, the study has at least 80% power with a two-tailed alpha = 5% to detect a 6 g/m² difference in LVMI change by CMRi, a 2.5 mL/m² in LAVI change by CMRi, a 2-unit difference in E/e' or e' using Tissue Doppler measurements.

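### The sample size for a t-test on change in LAVI rests on a baseline SD, its printed effect size does not compute, and no SD of change is given for the primary cMRI endpoint

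*Combined protocol and SAP*

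**What the plan says.** The sample size text stands in section 16.2 and, with the same figures, in the synopsis.

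- Test and error rates: "Setting alpha = 5% (two-tailed), beta = 20% and using an independent t-test to assess the change in LAVI over follow-up".
- Effect: a cited 36-week trial "observed a 36-week drop in LAVI of 2.6 mL/m²", and the plan takes this as the difference between arms by "assuming the control group shows no decrease in LAVI".
- Spread: the database subsample of 163 patients had "a baseline mean LAVI of 36.2 mL/m² (standard deviation of 6.9 mL/m²) determined by Doppler" echocardiography. No SD of change is given at this step.
- Effect size: "the expected effect size in a similar study is $2.6/6.5 = 0.38".
- Result: 222 evaluable patients (111 per arm), or 248 with 10% dropout, against a target of 250.

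A second paragraph, added by amendment, reports a blinded look at 125 patients with 9-month echocardiography, in whom "the actual standard deviation of baseline to 9-month change scores was 4.7". From this it draws an effect size of at least 2.0/5.0 = 0.40, says that 96 per group would be enough, and concludes that the study is adequately powered for echo LAVI. It then states at least 80% power for a 2.5 mL/m² difference in LAVI change by cMRI, without an SD.

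Section 10.2 makes cMRI LAVI change over 18 months the primary endpoint. Echo LAVI at 9 months is secondary endpoint 2.

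**The concern.** A two-sample t-test on change scores needs the SD of those change scores. A baseline SD measures something else: how much patients differ from one another at one visit. If the SD is the same at both visits, SD of change = baseline SD × √(2(1 − r)), where r is the correlation between baseline and follow-up. The two SDs are equal only at r = 0.5, which the plan does not state. Starting from 6.9, r = 0.3 gives 8.2 and r = 0.7 gives 5.3, so the substitution can err in either direction.

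Three further defects follow. The printed effect size is not the quotient of the two numbers shown. The later paragraph brings in 2.0 and 5.0 without a source. The endpoint that decides the trial has a detectable difference but no SD from which to check it. At stake are the stated sample size and power, and how readers judge a small or null difference in LAVI.

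**Working it through.** **Inputs** (section 16.2 unless noted): two-sided alpha 5%; power 80%; difference 2.6 mL/m²; baseline echo SD 6.9; printed divisor 6.5; blinded 9-month echo change SD 4.7 (125 patients); later figures 2.0 and 5.0; 111 per arm; dropout 10%; cMRI difference 2.5; primary endpoint from section 10.2.

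**Formulas.** With d = difference/SD:
- n per arm = 2(1.960 + 0.842)²/d² = 15.70/d²
- power ≈ Φ(d√(n/2) − 1.960)

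The exact t-test adds about one patient per arm. Power figures below are from the t-test.

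**1. Reproduce the plan.** 2.6/6.9 = 0.377, which rounds to 0.38. n = 15.70/0.377² = 110.6, so 111 per arm (112 by t-test), 222 in all. Dropout: 111/0.9 = 123.3, so 124 per arm, or 248. The stated figures follow from 6.9.

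**2. Try the printed divisor.** 2.6/6.5 = 0.400. n = 15.70/0.16 = 98.1, so 99 per arm (100 by t-test), 198–200 in all. The printed 6.5 reproduces neither 0.38 nor 111.

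**3. Echo LAVI with 111 evaluable per arm.**

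| Difference | SD | d | Power |
|---|---|---|---|
| 2.6 | 6.9 (baseline) | 0.377 | 79.8% |
| 2.6 | 4.7 (change) | 0.553 | 98.4% |
| 2.0 | 4.7 (change) | 0.426 | 88.4% |
| 2.0 | 5.0 (plan's later figure) | 0.400 | 84.3% |

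Difference detectable with 80% power at SD 4.7: 4.7 × 2.802 × √(2/111) = 1.77 mL/m² (1.78 by t-test).

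**4. Sampling error of the 4.7.** With n = 125, the 95% chi-square interval for the SD is about 4.2 to 5.4. At 5.4, power for 2.6 is 94.6% and the detectable difference is 2.04 mL/m².

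**5. The 96 per group.** An effect size of 0.40 needs 99–100 per arm, as in step 2. With 96 per arm, power is 78.7%.

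**6. The cMRI statement.** For 80% power at 2.5 mL/m² with 111 per arm, the SD of change may be at most 2.5/(2.802 × √(2/111)) = 6.6 mL/m². With all 125 per arm evaluable, the limit is 7.1. The plan gives no cMRI SD to set against these limits. As an illustration only, with 111 per arm, power for 2.5 would be 97.6% if the cMRI change SD were 4.7, and 76.7% if it were 6.9.

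**The case against.** The best defence is that section 16.2 already repairs itself. The amendment reports a true SD of change and re-bases the echo justification on it. The 5.0 may be 4.7 rounded up for caution, and it lies inside the interval of 4.2 to 5.4. Part of this stands: the plan does not ignore the change SD. But it gives no reason for moving from 2.6 to 2.0, it does not explain the 5.0, its 96 is slightly too low, and 222, 248 and 80% remain as the basis for the target.

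It is also fair to say that 6.9 as the divisor is inferred, since 6.5 is what is printed. The inference is strong, because 6.9 reproduces both 0.38 and 111, but the sponsor should confirm it.

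Some stronger readings are tempting, and the documents do not support them:

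- **The trial really has 98% power.** That figure pairs the 2.6 of the first paragraph with the 9-month echo SD of the second, a pairing the plan does not use. It does not apply to the primary endpoint, which differs in imaging method and in time.
- **The plan presents 2.6 mL/m² as the least it can detect.** The same section names 2.0 for echo and 2.5 for cMRI. For echo the fair comparison is 2.0 stated against about 1.8 computed, and 2.04 at the upper limit for the SD.
- **The trial's data disprove the 6.9.** A baseline SD of 6.9 with a change SD of 4.7 would imply r = 1 − 4.7²/(2 × 6.9²) = 0.77, but this mixes two cohorts. The 6.9 comes from database patients with BNP above 50 pg/mL in sinus rhythm. The trial admits BNP of 20–280 pg/mL, or patients by NT-proBNP (section 11.2.1).

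Finally, the timetable in section 25.1 puts the last 18-month visit in December 2020, so no enrolment decision can change. That stands. It is a reason to keep the initial calculation on record, not to leave its errors in place.

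**Conclusion.** The point holds in a limited form. The sample size for a test on change uses, on the only reading that reproduces it, a baseline SD, and the printed 2.6/6.5 = 0.38 is wrong as arithmetic. For echo LAVI the error is conservative: 111 per arm give about 98% power for 2.6 mL/m² rather than 80%, or 84–88% for the plan's later 2.0 mL/m². This assumes a t-test, 111 evaluable patients per arm and the blinded change SD of 4.7.

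It does not show an underpowered trial, and it does not establish the power of the primary analysis. That power is unknown from the documents. The claim of 80% power at 2.5 mL/m² is right only if the SD of 18-month cMRI change is at most about 6.6 with 111 per arm. The lack of that SD is the part that matters most for reading the main result.

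**What to change.** In section 16.2 and the synopsis:

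1. Keep the initial calculation as the record of how 250 was chosen. Reconcile 6.5, 6.9 and 0.38, and say that 6.9 is a baseline SD used in place of an SD of change.
2. Restate echo LAVI from the blinded change SD of 4.7: with 111 evaluable per arm, about 98% power for 2.6 mL/m², about 88% for 2.0, and 80% for about 1.8.
3. Give the basis of 2.0 and 5.0, or delete them.
4. If the effect size of 0.40 stays, correct 96 per group to 99–100.
5. State the SD of 18-month cMRI LAVI change behind the 2.5 mL/m² claim, using the pooled SD over both arms, without treatment codes, from scans already taken.

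Leave enrolment at 250. The cost is wording and one blinded calculation, with no added patients or procedures. The small downside is that the stated justification for the sample size changes.
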